- (BMS-986183 and nivolumab dose escalation [Part 3] only) Grade 2 or greater eye pain or reduction of visual acuity that does not respond to topical therapy and does not improve to Grade 1 severity within 2 weeks of starting therapy or requires systemic treatment.
- \geq Grade 3 nonhematologic toxicity, with the following exceptions.

The following Grade 3 or greater nonhematologic events will NOT be considered DLTs:

- ≥ Grade 3 electrolyte abnormalities that are not complicated by associated clinical AEs, are not clinically significant, last less than 72 hours and either resolve spontaneously or respond to conventional medical intervention
- Grade 3 nausea, vomiting or diarrhea that lasts less than 48 hours and either resolves spontaneously or responds to conventional medical intervention
- Isolated Grade 3 fever not associated with hemodynamic compromise (ie, hypotension, clinical or laboratory evidence of impaired end-organ perfusion)
- Grade 3 or 4 elevation of amylase or lipase not associated with clinical or radiographic evidence of pancreatitis

- Grade 3 endocrinopathy that is well controlled by hormone replacement
- Grade 3 fatigue for \leq 7 days
- Grade 3 infusion reaction that returns to Grade 1 in less than 6 hours

Hematologic DLT

- Grade 4 neutropenia \geq 7 days in duration
- Grade 4 febrile neutropenia of any duration
- Grade 3 febrile neutropenia that lasts > 48 hours
- Grade 4 thrombocytopenia or Grade \geq 3 thrombocytopenia associated with clinically significant bleeding
- Grade 4 anemia

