- For an AE requiring dose modification, BMS-986183 should be interrupted to allow recovery from the AE. Re-initiation of study drug cannot occur until AE decreases to ≤ Grade 1 or baseline assessment. In case of delayed recovery to ≤ Grade 1 or baseline (except for alopecia or fatigue) from treatment-related AEs that results in a delay of treatment for > 6 weeks, the subject will not receive additional protocol-related therapy and will be removed from study unless discussed and agreed upon by the Sponsor/medical monitor and investigators that it is in the best interest of the subject to receive additional therapy with BMS-986183 (for example, if the subject has demonstrated a response to therapy).
- During the DLT evaluation period, if a subject is dose reduced and experiences a DLT at the lower dose, this DLT will be attributed to the highest dose level administered.
- Dose reductions for nivolumab will not be permitted for individual subjects.

For data collection and analysis purposes, all subjects will continue to be classified by the original treatment arm.

Dose Modification Criteria for Drug-Related Adverse Events	BMS-986183 (modification at next dose)
Grade 4 neutropenia lasting > 5 days	Decrease 1 level
Grade 3 febrile neutropenia lasting > 48 hours	Decrease 1 level
Grade 4 febrile neutropenia	Discontinue
Grade 4 thrombocytopenia or ≥ Grade 3 thrombocytopenia with significant bleeding	Decrease 1 level
QTcF > 500 msec confirmed by at least 1 repeat ECG and at least 60 msec above baseline	Interrupt if needed to optimize electrolyte management. If persists after electrolyte optimization (including dose modification of BMS-986183, if necessary), discontinue.
Grade 1 Troponin I or T confirmed when repeated in 72 hours	Discontinue
Grade 3 Troponin I or T	Discontinue
AST/ALT/total bilirubin elevation per Section 4.5.3	Decrease 1 level
\geq Grade 3 infusion-related reaction	See Section 3.7
\geq Grade 3 peripheral neuropathy	Discontinue
Any other drug-related \geq Grade 3 nonhematologic AE except in subjects not receiving maximum medical management or electrolyte abnormalities that may be managed with supplements	Decrease 1 level

Table 4.5.2-1:Dose Modifications

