4.5.6 Guidelines for Permanent Discontinuation

Subjects will be required to permanently discontinue study drug for the following criteria:

- Clinical deterioration, as assessed by the investigator
- Progressive disease (PD)
- For subjects in BMS-986183 and nivolumab dose escalation (Part 3) and BMS-986183 and nivolumab dose expansion (Part 4), any Grade 2 drug-related uveitis, eye pain, or blurred vision that does not respond to topical therapy and does not improve to Grade 1 severity within the retreatment period OR requires systemic treatment
- Any drug-related AE occurring at any time that meets DLT criteria as outlined in Section 4.5.1 will require discontinuation of nivolumab and/or dose modification of BMS-986183.
- Grade 3 drug-related uveitis, pneumonitis, bronchospasm, hypersensitivity reaction, neurological toxicity, or infusion reaction of any duration requires discontinuation.
- Any Grade 3 non-skin, drug-related AE lasting > 7 days or recurs.
- Any Grade 3 or 4 AE that meets DLT criteria as outlined in Section 4.5.1; however, an exception may be made for the following upon consultation between the investigator and BMS medical monitor:
 - Grade 3 infusion reaction that returns to Grade 1 in less than 6 hours
 - Grade 3 diarrhea, nausea, vomiting, or abdominal pain that returns to Grade 1 or baseline within 3 days with medical intervention
 - Grade 3 pruritus or rash that returns to Grade 1 or baseline within 7 days with medical intervention
 - Grade 3 or 4 electrolyte imbalances/abnormalities that are not associated with clinical sequelae and are corrected with supplementation/appropriate management within 72 hours
 - Grade 4 neutropenia < 7 days in duration
 - Grade 4 lymphopenia or leukopenia
 - Grade 3 or 4 amylase or lipase abnormalities that are not associated with symptoms or clinical manifestations of pancreatitis
 - Grade 3 or 4 drug-related endocrinopathy AEs, such as hyper- or hypothyroidism, or glucose intolerance, which resolve or are adequately controlled with physiologic hormone replacement (corticosteroids, thyroid hormones) or glucose-controlling agents, respectively, may not require discontinuation after discussion with and approval from the BMS Medical Monitor. Adrenal insufficiency requires discontinuation regardless of control with hormone replacement.
 - Grade 3 drug-related laboratory abnormalities do not require treatment discontinuation except:

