 - Grade 3 drug-related thrombocytopenia > 7 days or associated with bleeding requires discontinuation
 - AST or ALT > $10 \times ULN$ for > 2 weeks
 - AST or ALT > $15 \times$ ULN irrespective of duration

- Total bilirubin > 8 × ULN irrespective of duration for subjects with elevated bilirubin at study entry or > 5 × ULN for those with normal total bilirubin at entry
- Concurrent AST or ALT > 3 × ULN and total bilirubin > 5 × ULN for subjects entering treatment with a normal bilirubin and up to 8 × ULN for subjects with elevated bilirubin
- Any AE, laboratory abnormality, or intercurrent illness that, in the judgment of the investigator, presents a substantial clinical risk to the subject with continued dosing of study treatment(s).
- Confirmed CR
- Completion of 1 year (17 cycles, with 21 days/cycle) of treatment

All subjects who discontinue IP should comply with protocol-specified follow-up procedures as outlined in Section 5.1. The only exception to this requirement is when a subject withdraws consent for all study procedures including post-treatment study follow-up or loses the ability to consent freely (eg, is imprisoned or involuntarily incarcerated for the treatment of a psychiatric or physical illness).

If study treatment is discontinued prior to the subject's completion of treatment, the reason for the discontinuation must be documented in the subject's medical records and entered on the appropriate CRF page.

If the investigator determines a possible favorable benefit/risk ratio that warrants continuation of study drug(s), a discussion between the investigator and the BMS Medical Monitor/designee must occur including during BMS-986183 and nivolumab combination therapy. If there is toxicity requiring discontinuation and the toxicity is considered related to 1 study drug while clinical benefit has been observed (eg, pneumonitis due to nivolumab), treatment with the study drug to which the toxicity is attributed must be discontinued, but may be resumed for the other study drug, but only after discussion and agreement with the BMS Medical Monitor (or designee).

The consideration to re-initiate study therapy under these exceptions will be made on a case-by-case basis after considering the overall benefit/risk profile and in consultation between the investigator and the study Sponsor.

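### Table 4.5.2-1 and Section 4.5.6 give different actions for the same severe toxicities without settling which governs; the infusion-reaction and troponin rules also conflict

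*Protocol*

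**What the plan says.** Protocol Section 4.5.6 lists for permanent discontinuation "Any Grade 3 or 4 AE that meets DLT criteria as outlined in Section 4.5.1; however, an exception may be made" for a set of named events, after consultation with the medical monitor.

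Section 4.5.1 defines the hematologic DLTs. They include "Grade 3 febrile neutropenia that lasts > 48 hours", Grade 4 neutropenia of 7 days or more, Grade 4 thrombocytopenia, and Grade 3 or worse "thrombocytopenia associated with clinically significant bleeding".

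Table 4.5.2-1 in Section 4.5.2 assigns a reduction of one dose level to "Grade 3 febrile neutropenia lasting > 48 hours", to Grade 4 thrombocytopenia or at least "Grade 3 thrombocytopenia with significant bleeding", to "Grade 4 neutropenia lasting > 5 days", and, in its last row, to any other drug-related nonhematologic AE of Grade 3 or worse, with limited exclusions.

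Among the 4.5.6 exceptions is "Grade 4 neutropenia < 7 days in duration". Grade 3 laboratory abnormalities are also excepted, but with a carve-back: "Grade 3 drug-related thrombocytopenia > 7 days or associated with bleeding requires discontinuation". A separate 4.5.6 bullet stops Grade 3 non-skin drug-related AEs that last more than 7 days or come back.

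For infusion reactions the table refers to Section 3.7. For a Grade 1 troponin rise it uses a 72-hour repeat, whereas Sections 4.5.4 and 5.3 require the repeat within 24 hours.

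**The concern.** The same event leads to a lower dose in one section and to permanent discontinuation in another. This is a first-in-human study (Section 1.4.4) with no data monitoring committee (Section 7), so the written toxicity rules carry much of the protection. Sites reading different sections could treat the same serious toxicity differently. The specific risk is that a site follows the table and re-doses at a lower level without recognising that a 4.5.6 criterion, and hence a discussion with the medical monitor, applies.

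The analysis is touched as well. AEs leading to discontinuation are part of the primary endpoint (Protocol 8.3.1, SAP 4.1), and the SAP (7.5) classifies them by the action recorded on the CRF. Which section a site follows decides whether the event appears in the output of SAP 7.5.4 (discontinuation) or of 7.5.5 (delay, interruption or reduction).

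**Working it through.** The plan states no figure to reproduce. The check compares the sections event by event.

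**Step 1: table against 4.5.6**

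| Event | Table 4.5.2-1 | Section 4.5.6 | Agree? |
|---|---|---|---|
| Grade 3 thrombocytopenia with bleeding | Reduce | Stop, named explicitly | No |
| Grade 4 thrombocytopenia (DLT) | Reduce | Stop; the laboratory exception covers Grade 3 only | No |
| Grade 3 febrile neutropenia > 48 h (DLT) | Reduce | Stop; not named among the exceptions | No |
| Grade 4 neutropenia, 7 days or more (DLT) | Reduce; the row has no upper limit | Stop; the exception ends below 7 days | No |
| Grade 4 neutropenia, 6 days | Reduce | Excepted | Yes |
| Other Grade 3 nonhematologic AE that is an unexcepted DLT, or is non-skin and lasts > 7 days or recurs | Reduce | Stop | No |
| Grade 4 febrile neutropenia; Grade 3 or worse neuropathy | Stop | Stop | Yes |
| AST, ALT, bilirubin | Reduce, per 4.5.3 | Stop at listed values | Reconciled: 4.5.3.2 defers to 4.5.6 |

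For Grade 4 neutropenia the table starts above 5 days and the exception ends below 7. In whole days only a 6-day episode fits both.

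The table's last row also takes in Grade 4 nonhematologic events. A 4.5.2 bullet already removes those from therapy unless continuation is agreed, apart from electrolyte abnormalities, which it refers to the table. Another 4.5.2 bullet leaves open a second reduction when a severe nonhematologic AE recurs despite a reduction, whereas 4.5.6 stops a recurrent Grade 3 non-skin AE.

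**Step 2: which section governs?**

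- Favouring 4.5.6: Section 4.5.4 says that subjects meeting its criteria must stop, and that only the others resume. Section 4.5.5 limits resumption to AEs that do not meet it.
- Favouring the table: Section 3.5, the mandatory discontinuation list, sends AE-driven stops to 4.5.2, and Section 3.1 names 3.5 as the place for discontinuation criteria. Section 4.5.2 handles DLT-level AEs through the table and its own text. One bullet in 4.5.6 itself answers a drug-related DLT-level AE by stopping nivolumab and/or modifying the BMS-986183 dose, which could mean stopping or continuing lower.
- Neutral: 4.5.2 calls its criteria general guidelines, but the title of 4.5.6 also says guidelines.

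**Step 3: Grade 3 infusion reaction resolving within 6 hours**

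Three places treat this case leniently: the later text of 3.7 (premedicate future infusions), 4.5.1 (not a DLT) and the 4.5.6 exception list. Two sentences contradict them: one in 3.7 stops all study drugs for Grade 3 or 4, and one bullet in 4.5.6 stops Grade 3 whatever its duration. The 4.5.6 exception hangs under the DLT bullet, which does not reach an event that 4.5.1 excludes from DLTs. The bullet that does stop it has no exception.

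**Step 4: Grade 1 troponin**

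72 − 24 = 48 hours' difference in the retest. All three places stop the drug if the rise is confirmed. A rise still above normal at 24 hours but normal at 72 would be stopped under 4.5.4 and need not be under the table, if its repeat is taken at 72 hours.

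**Step 5: shift per subject handled differently**

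The shift is 1/N, using the planned numbers in Protocol 3.1 and 8.1:

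- Expansion part: 1/50 = 2.0 percentage points
- Part 1: 1/30 = 3.3
- Part 3: 1/21 = 4.8

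The SAP also tabulates by treatment, meaning dose level. At the planned 3 to 6 subjects per dose level in Part 3, one subject is 1/6 = 16.7 to 1/3 = 33.3 points.

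**The case against.** The strongest reply is that the order can be worked out. Sections 4.5.4 and 4.5.5 make resumption conditional on not meeting 4.5.6, study drug is held for any potential DLT, and 4.5.6 allows continuation only after discussion with the medical monitor. This softens the conflict. It does not remove it, because a site that starts from 3.1 or 3.5 reaches the table without being sent to 4.5.6.

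The opposite reading is also tempting: that the table states the wrong default. The documents do not support that. Section 3.5, the lead-in of 4.5.2 and the dose-modification bullet in 4.5.6 are all consistent with reduction as the intended action for BMS-986183. What is shown is that two sections differ. Which action is right is a clinical decision.

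On infusion reactions, the more specific later sentences of 3.7 make the intended 6-hour rule readable, so that part is mainly faulty drafting. On troponin, drug is held meanwhile and the end action is the same, so that part is minor.

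The per-subject shifts would apply to any single reclassified event. They show sensitivity, not expected impact.

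**Conclusion.** The inconsistency is real and should be corrected. Five groups of events carry a reduction in the table and a stop in 4.5.6: bleeding thrombocytopenia, Grade 4 thrombocytopenia, febrile neutropenia beyond 48 hours, Grade 4 neutropenia of 7 days or more, and the unexcepted, prolonged or recurrent Grade 3 nonhematologic AEs. The case against the febrile neutropenia row assumes that it is not read into the Grade 3 laboratory exception, which does not name it. The hepatic row is not part of the finding.

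The documents give no frequency for these events, so the number of subjects affected cannot be estimated. The effect on the analysis is a move between two descriptive outputs. No event is lost, and no test or power is affected.

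A reader might go further in two ways. One is to infer that dose-escalation decisions are distorted. They are not shown to be: DLTs are counted by the 4.5.1 definition, whatever action follows. The other is to infer that the Part 2 and Part 4 enrolment-pause rules (above 29% and 31%) would be miscounted. Those rules count drug-related AEs requiring dose modification and do not say whether stopping counts, so no effect can be asserted.

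**What to change.** 1. State in 4.5.2 and 3.5 that 4.5.6 overrides Table 4.5.2-1, with any continuation only after medical-monitor agreement and at one dose level lower. This is the safer reading and the one that 4.5.4 and 4.5.5 support. Align the 4.5.6 bullet that permits BMS-986183 dose modification.
2. Change the thrombocytopenia and febrile neutropenia (> 48 h) rows to match 4.5.6. Split the Grade 4 neutropenia row: above 5 and below 7 days, reduce one level; 7 days or more, discontinue.
3. Make the last table row apply only when no 4.5.6 criterion is met, keeping Grade 4 electrolyte abnormalities covered. Reconcile the 4.5.2 bullet on recurrence despite dose reduction with the recurrence criterion in 4.5.6.
4. Limit the blanket stopping sentence in 3.7 to Grade 4 and to Grade 3 reactions not resolved within 6 hours. Move the under-6-hour exception into the 4.5.6 bullet that stops Grade 3 reactions regardless of duration.
5. Set the troponin repeat in the table to within 24 hours.

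The cost is protocol wording, with no change to sample size, data collection or the SAP. Because the actions for serious toxicities change, it needs the sponsor's clinical agreement and an amendment approved by the IRB/IEC (Section 9.1.1).

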4.5.7 Treatment Beyond Disease Progression in BMS-986183 and Nivolumab Combination Therapy

Accumulating evidence indicates a minority of subjects treated with immunotherapy may derive clinical benefit despite initial evidence of PD.⁴⁶

Subjects treated with BMS-986183 and nivolumab combination therapy may be permitted to continue combination therapy beyond initial RECIST v1.1-defined PD, as assessed by the investigator, as long as they meet the following criteria:

- Investigator-assessed clinical benefit
- Tolerance of study drug
- Stable performance status

- Treatment beyond progression will not delay an imminent intervention to prevent serious complications of disease progression (eg, central nervous system [CNS] metastases).
- Subject provides written informed consent prior to receiving additional combination treatment. All other elements of the main consent including description of reasonably foreseeable risks or discomforts, or other alternative treatment options will still apply.

A radiographic assessment/scan should be performed within 6 weeks of initial investigatorassessed progression to determine whether there has been a decrease in the tumor size or continued PD. The assessment of clinical benefit should be balanced by clinical judgment as to whether the subject is clinically deteriorating and unlikely to receive any benefit from continued treatment with combination therapy.

If the investigator deems that the subject continues to achieve clinical benefit by continuing treatment, the subject should remain on the study and continue to receive monitoring according to the Table 5.1-2.

Discontinuation due to Further Progression (Confirmed Progression)

For the subjects who continue combination therapy beyond progression, further progression is defined as an additional 10% increase in tumor burden with a minimum 5 mm absolute increase from time of initial PD. This includes an increase in the sum of diameters of all target lesions and/or the diameters of new measurable lesions compared to the time of initial PD. Combination therapy should be discontinued permanently upon documentation of further progression.

New lesions are considered measureable at the time of initial progression if the longest diameter is at least 10 mm (except for pathological lymph nodes, which must have a short axis of at least 15 mm). Any new lesion considered nonmeasureable at the time of initial progression may become measureable and therefore included in the tumor burden if the longest diameter increases to at least 10 mm (except for pathological lymph nodes, which must have a short axis of at least 10 mm (except for pathological lymph nodes, which must have a short axis of at least 10 mm (except for pathological lymph nodes, which must have a short axis of at least 15 mm). In situations where the relative increase in total tumor burden by 10% is solely due to inclusion of new lesions, which become measurable, these new lesions must demonstrate an absolute increase of at least 5 mm. The criteria for progression during treatment beyond progression are for subject management purpose only. Statistical analysis of efficacy will be based on RECIST v1.1.

4.6 Blinding/Unblinding

Not applicable.

4.7 Treatment Compliance

Study drug will be administered in the clinical facility by qualified medical personnel. The investigator and the study personnel will ensure that each subject receives the calculated dose of the study drug. Treatment compliance will be monitored by drug accountability, as well as recording BMS-986183 and nivolumab administration in subjects' medical records and CRF. Drug supplies will be inventoried and accounted for throughout the study. The Drug Accountability Log should be reviewed by the study monitor during site visits and will be at the completion of the study. Any discrepancy should be brought to the attention of the Sponsor.

4.8 Destruction of Study Drug

For this study, study drugs (those supplied by BMS or sourced by the investigator) such as partially used study drug containers, vials, and syringes may be destroyed on site.

Any unused study drugs can only be destroyed after being inspected and reconciled by the responsible BMS study monitor unless study drug containers must be immediately destroyed as required for safety, or to meet local regulations (eg, cytotoxics or biologics).

On-site destruction is allowed provided the following minimal standards are met:

- On-site disposal practices must not expose humans to risks from the drug.
- On-site disposal practices and procedures are in agreement with applicable laws and regulations, including any special requirements for controlled or hazardous substances.
- Written procedures for on-site disposal are available and followed. The procedures must be filed with the site's Standard Operating Procedures and a copy provided to BMS upon request.
- Records are maintained that allow for traceability of each container, including the date disposed of, quantity disposed, and identification of the person disposing the containers. The method of disposal, (ie, incinerator, licensed sanitary landfill, or licensed waste disposal vendor) must be documented.
- Accountability and disposal records are complete, up-to-date, and available for the monitor to review throughout the clinical study period.

If conditions for destruction cannot be met the responsible BMS study monitor will make arrangements for return of study drug.

It is the investigator's responsibility to arrange for disposal of all empty containers, provided that procedures for proper disposal have been established according to applicable federal, state, local, and institutional guidelines and procedures, and provided that appropriate records of disposal are kept.

4.9 Return of Study Drug

If study drug will not be destroyed upon completion or termination of the study, all unused and/or partially used study drug that was supplied by BMS must be returned to BMS. The return of study drug will be arranged by the responsible study monitor.

It is the investigator's responsibility to arrange for disposal of all empty containers, provided that procedures for proper disposal have been established according to applicable federal, state, local, and institutional guidelines and procedures, and provided that appropriate records of disposal are kept.

